### Power Analysis

The power analysis was based on data from our previous pilot study (Brokaw 2014). To address Hypothesis I, we calculated power to detect significant gains after only the robotic training. Using the pre-post changes after the initial period of robotic therapy from our pilot study, the effect size for the ARAT was  $d_z=1.2$ , with pre-post correlation  $r=0.94$ . In order to detect an effect this large, when using a 1-tailed paired t-test with  $\alpha=.05$ , a sample size of **N=8** is required for power > 0.90 (Faul 2009). For the Fugl-Meyer, the effect size was  $d_z=0.74$ , with pre-post correlation  $r=0.85$ , which would require a sample size of **N=18** for power > 0.90.

To power Hypothesis II, the pre-post effect size for gains on the ARAT after the experimental treatment (12 hours of robot + 12 hours of conventional therapy) was  $d_z=0.77$ , with pre-post correlation  $r=0.95$  (only using data from subjects who received robotic therapy followed by conventional therapy). In order to detect an effect this large, when using a 1-tailed paired t-test with  $\alpha=.05$ , a sample size of **N=16** is required for power > 0.90. For the Fugl-Meyer, the pre-post effect size was  $d_z=1.41$ , with pre-post correlation  $r=0.91$ . In order to detect this difference, only **N=6** subjects are required for power > 0.90.

To address Hypothesis III, we calculated the power to detect the expected differences in gains between the experimental and control groups. The experimental treatment in our pilot study produced gains of 7 (sd=4.9) in the Fugl-Meyer. A recent study reported gains of 2.47 (sd=1.67) on the Fugl-Meyer after 24 hours of conventional therapy in 35 stroke subjects with similar intake Fugl-Meyer scores as in our pilot study (FM = 22.4 vs. 21) (Klamroth-Marganska 2014). Using these data, the mean difference in treatments will have an effect size of 1.9. For a 1-tailed unpaired t-test, **N=5** subjects in each treatment group are needed to detect this difference with power > 0.80. Similarly for the ARAT, we had gains of 5.6 (sd=4.7) after the experimental treatment in our pilot study. A different study (Fleming 2015) reported gains of 1.0 (sd=5.7) after 24 hours of conventional therapy in 17 chronic stroke subjects with similar intake ARAT scores as in our pilot study (ARAT = 26.6 vs. 20.9). Using these data, the mean difference in treatments will have an effect size of 0.84. For a 1-tailed unpaired t-test, **N=19** subjects in each treatment group will detect this difference with power > 0.80.

Therefore with **N=19** subjects in each treatment group, we will detect the anticipated pre-post changes and group differences in the ARAT and Fugl-Meyer. We had a dropout rate of 0.167 in the pilot study. Therefore, we will plan for this and recruit 23 subjects into each treatment group. We have no pilot data on the MAL to perform a power analysis for the outcome.

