## 3. Aims / Hypotheses

Specific AIM: We will perform a clinical trial to compare the effectiveness of robotic training to conventional therapy from an occupational therapist. To take advantage of the facilitatory effect of robot therapy on subsequent conventional therapy, the experimental treatment will be 12 hours of robot therapy followed by 12 hours of conventional therapy. Chronic stroke

subjects (N=46) will be randomly assigned to receive this experimental treatment or 24 hours of conventional therapy from an occupational therapist.

**Hypothesis I:** Gains from the initial 12 hours of robotic therapy will be significant ( $p < 0.05$ ) in the domains of impairment (Fugl-Meyer), function (Action Research Arm Test) and amount of arm use (Motor Activity Log).

**Hypothesis II:** Gains in impairment, function and arm use in the experimental group (robot + conventional therapy) will be significant ( $p < 0.05$ ) and clinically important (defined as greater than 10% gain) immediately after all treatments and also at the 6-month follow-up.

**Hypothesis III:** Gains in impairment, function and arm use will be significantly greater in the experimental group (robot + conventional therapy) than the conventional therapy control group immediately after the end of all treatments and also at the 6-month follow-up.

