### Data analysis

Prior to conducting the main analyses, summary statistics, histograms, and scatter plots will be inspected to verify that distribution assumptions are met. Adjustments (e.g., transformations) to the main dependent measures will be made as necessary to address any problems (e.g., skewness, outliers) that these preliminary analyses uncover. To test Hypotheses, a series of mixed model ANOVAs will be tested, one for each dependent variable, with the within-subject variable being timepoint (pre, after 12 hours of treatment, after 24 hours of treatment, 6 month followup) and the between-subject variable of group (experimental vs. control). A significant effect of timepoint or a significant timepoint x group interaction would be followed with a series of paired t-tests, with Bonferoni corrections. Hypothesis I will be tested with a paired t-test between the pre and post-robotic timepoint (after 12 hours of robotic treatment). Hypothesis II will be tested with a paired t-test between the pre and post-treatment timepoint in the experimental group (after 12 hours of robot and 12 hours of conventional therapy). Additionally a z-test will be performed for the hypothesis that the proportion of subjects with 10% or greater gain at the post-treatment timepoint is significantly greater than zero. A final paired t-test and z-test between pre and 6-month followup timepoints will be performed. If a change is statistically significant, mean changes will be compared to predetermined MCID values of 10% of full scale. To test Hypothesis III, the timepoint x group interaction effect will be examined in the mixed model ANOVA. If significant, gains in the dependent variables will be calculated at the post-treatment and 6-month timepoints (relative to the pre timepoint), and between-group differences will be tested with unpaired t-tests, with Bonferoni corrections.

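### The power above 0.90 stated for the Hypothesis I Fugl-Meyer test assumes one uncorrected one-tailed test and does not carry over to the Bonferroni-corrected paired tests in the Data analysis section

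*Combined protocol and SAP*

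**What the plan says.** Section 3 (Aims / Hypotheses) states Hypothesis I as: "Gains from the initial 12 hours of robotic therapy will be significant", with p < 0.05, for the Fugl-Meyer, the ARAT and the Motor Activity Log. It does not say whether that p-value is adjusted.

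The Data analysis part of section 5 specifies a mixed model ANOVA for each dependent variable. A significant timepoint effect or timepoint-by-group interaction "would be followed with a series of paired t-tests, with Bonferoni corrections". The paired tests for the hypotheses follow immediately:

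- Hypothesis I compares pre with 12 hours of robot treatment: "Hypothesis I will be tested with a paired t-test between the pre and post-robotic timepoint (after 12 hours of robotic treatment").
- Hypothesis II compares pre with 24 hours: "Hypothesis II will be tested with a paired t-test between the pre and post-treatment timepoint in the experimental group".
- The follow-up comparison comes next: "A final paired t-test and z-test between pre and 6-month followup timepoints will be performed".

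The section gives neither a number of comparisons nor a sidedness for any of these tests.

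The Power Analysis part of section 5 sizes Hypothesis I "when using a 1-tailed paired t-test with" alpha = .05, with no adjustment for multiplicity. For the Fugl-Meyer, with dz = 0.74, it gives an effect "which would require a sample size of N=18 for power > 0.90". It closes by saying that with 19 subjects per group "we will detect the anticipated pre-post changes and group differences in the ARAT and Fugl-Meyer".

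**The concern.** The power calculation and the analysis section describe the same paired test under different rules. One uses the full 0.05 in a single one-tailed test. The other, read in order, puts the test in a Bonferroni-corrected series. If the correction applies, each test is held to a smaller level and the stated power is too high. The closing claim that 19 per group will detect the pre-post changes inherits the problem.

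The success rule is also left open. Suppose the Fugl-Meyer gain gives an unadjusted p of 0.03. It meets Hypothesis I if the Aims mean an unadjusted p-value. It fails if the correction covers this test, because even two comparisons set the threshold at 0.05/2 = 0.025. A divisor and sidedness not fixed in advance could be settled after the data are seen.

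**Working it through.** **Inputs.** The effect sizes are the pilot values in the Power Analysis: Fugl-Meyer dz = 0.74 and ARAT dz = 1.2 for Hypothesis I; ARAT dz = 0.77 and Fugl-Meyer dz = 1.41 for Hypothesis II. The number of completers is 19 per group (Power Analysis; 38 in total under Recruitment). Alpha is 0.05. The Bonferroni divisor k is not given, so a range is shown.

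**Formula.** For a paired t-test with n subjects, the statistic has a noncentral t distribution with n − 1 degrees of freedom and noncentrality dz × √n. One-tailed power is the probability that it exceeds the upper 0.05/k point of the central t. The two-tailed version uses the 0.05/(2k) point in each tail.

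**Reproducing the plan (one-tailed, k = 1).**

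- Fugl-Meyer, Hypothesis I, n = 18: noncentrality 0.74 × √18 = 3.14, critical value 1.740 on 17 df, power 0.914. At n = 17 the power is 0.899, so 18 is the smallest n that reaches 0.90.
- ARAT, Hypothesis I, n = 8: 0.919. ARAT, Hypothesis II, n = 16: 0.902. Fugl-Meyer, Hypothesis II, n = 6: 0.903.

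All four paired-test sample sizes reproduce, which confirms that the plan used the exact one-tailed, uncorrected calculation.

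**Hypothesis I Fugl-Meyer at 19 completers.** Noncentrality is 0.74 × √19 = 3.23 on 18 df. The one-tailed critical values are 1.734 (k = 1), 2.101 (k = 2), 2.304 (k = 3) and 2.639 (k = 6).

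| Comparisons (k) | Level per test | Power, one-tailed | Power, two-tailed |
|---|---|---|---|
| 1 (uncorrected) | 0.05 | 0.93 | 0.86 |
| 2 | 0.025 | 0.86 | 0.78 |
| 3 | 0.0167 | 0.81 | 0.72 |
| 6 | 0.0083 | 0.72 | 0.61 |

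The divisor of 3 counts the experimental-group tests that the Data analysis section names for each outcome: pre against 12 hours, 24 hours and 6 months. The divisor of 6 counts all pairs of the four timepoints. Pooling three tests over three outcomes (k = 9) gives 0.65 one-tailed and 0.54 two-tailed. Only the uncorrected one-tailed entry exceeds 0.90.

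**Other paired tests at 19 completers.**

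- Hypothesis II ARAT (dz = 0.77): 0.94 one-tailed uncorrected; with k = 3, 0.84 one-tailed and 0.76 two-tailed.
- Hypothesis I ARAT (dz = 1.2): with k = 6, 0.99 one-tailed and 0.98 two-tailed.
- Hypothesis II Fugl-Meyer (dz = 1.41): above 0.99 in all these cases.

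**The case against.** Several points on the other side have force.

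- **The arithmetic is right.** A reader might infer that N = 18 is a miscalculation. It is not; it is correct for its stated inputs. The fault is a mismatch between two sections.
- **Whether the correction reaches Hypothesis I is not explicit.** The sentences for Hypotheses I and II do not mention Bonferroni, whereas the sentence for Hypothesis III repeats it. An exemption is therefore possible. But the Hypothesis I test is named immediately after the corrected series is introduced, and nothing exempts it, so inclusion is the more natural reading. If an exemption is meant, it has to be written.
- **No divisor is given.** It would be tempting to present 0.72 to 0.81 as the result of the plan's own rule. That range depends on assuming three comparisons. What does not depend on the assumption is that any divisor of 2 or more brings power below 0.90.
- **Sidedness.** The only sidedness stated for this test is one-tailed, in the Power Analysis, and the hypothesis is directional. A reader might infer two-tailed testing from the pilot results in the Background. The pilot SD and ± value imply n of about (4.9/2.2)² = 4.96, so 5 subjects; 7/2.2 = 3.18 on 4 df gives a two-tailed p of 0.033, against 0.034 stated. This shows how the pilot was reported, not how this trial will be analysed. The two-tailed column is therefore a conditional alternative.
- **Thresholds.** A reader might see three conflicting thresholds in three sections. The Aims and the Power Analysis share 0.05, and p < 0.05 in the Aims could be an adjusted p-value. Only the corrected series departs from the level used for the power.
- **Consequence.** The 19 per group is set by the between-group ARAT comparison under Hypothesis III. With one-tailed tests and three comparisons, Fugl-Meyer power is still 0.81, above the 0.80 used for that comparison. The documents do not support a conclusion that the trial is too small because of this point.

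**Conclusion.** The point holds as an inconsistency between the power section and the analysis plan, and it should be fixed. The power above 0.90 for the Hypothesis I Fugl-Meyer test belongs to a single uncorrected one-tailed test and does not carry over to a Bonferroni-corrected one. At 19 completers, one-tailed power drops from 0.93 to 0.86, 0.81 or 0.72 with 2, 3 or 6 comparisons; two-tailed testing would give 0.78, 0.72 or 0.61. The Hypothesis II ARAT test is affected to a similar degree, and the other two paired tests hardly at all.

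This rests on reading the correction as covering the Hypothesis I and II paired tests, on an assumed divisor, and on the pilot effect sizes as given. The figures also leave out the requirement that an ANOVA effect be significant first, which could only lower them. The effect is modest: it changes the power that can be claimed for within-group tests and leaves the sample size as it is.

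**What to change.** 1. In Data analysis, state whether the Hypothesis I and II paired t-tests are Bonferroni-corrected, over how many comparisons, and whether they are one- or two-tailed.
2. In section 3, say whether p < 0.05 is the adjusted p-value.
3. In Power Analysis, restate the paired-test power at N = 19 under that rule. For example: Fugl-Meyer, Hypothesis I, 0.81 one-tailed with three comparisons; ARAT, Hypothesis II, 0.84 on the same basis. If the tests are to be one-tailed and uncorrected, say so in Data analysis; 0.93 and 0.94 then apply.
4. Tie the closing statement that 19 per group will detect the pre-post changes to the restated figures.

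No extra patients, visits or analyses are needed. The only cost is a less favourable stated power if the correction or two-tailed testing is confirmed.

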#### **4. Background**

Approximately 795,000 individuals in the United States have a stroke each year (Go 2014). Approximately 15,000 veterans are hospitalized for stroke each year (<http://www.queri.research.va.gov/str/>), with costs of \$75 million for post-acute inpatient care and \$88 million annually for follow-up care ([http://www.queri.research.va.gov/about/factsheets/stroke\\_factsheet.pdf](http://www.queri.research.va.gov/about/factsheets/stroke_factsheet.pdf)). Fifty percent of stroke survivors older than 64 have persistent hemiparesis at six months post-stroke and 26% are dependent in activities of daily living (ADL) (Roger 2012). In the upper extremity, reaching and grasping movements are often impaired and a focus of rehabilitation. Impairments include decreased muscle activation and weakness (Zackowsky 2004, Gowland 1992), disrupted interjoint coordination (Cirstea 2003, Beer 2000), decreased smoothness of movement (Rohrer 2002, Krebs 1999), and dyscoordination between reach and grasp movements (van Vliet 2007). Limitations in ADL ability and decreased quality of life can result from even mild impairments in upper-limb function (Nichols-Larsen 2005, [name] 2006).

In a pilot clinical trial funded by the Department of Veterans affairs, we found that the robotic exoskeleton elicited improvements in arm function that can potentially supplement conventional methods to improve outcomes (Brokaw 2014). The robot has 5 active motors that assist with 3 shoulder DOF, elbow flexion/extension and supination/pronation (Fig. 1). A passive hand orthosis (HandSOME) is worn to assist with opening the hand. Twelve chronic stroke subjects were randomized to 12 hours of robotic or conventional therapy and then crossed over to the other therapy type after a 1 month washout period. Across the 3 month study period, subjects showed significant improvements in the Fugl-Meyer Test of Motor Function ( $p = 0.013$ ) and Box and Blocks tests ( $p = 0.028$ ). The Fugl-Meyer (Fugl-Meyer 1975) tests impairment throughout the upper extremity, while the Box and Blocks (Platz 2005) scores the number of one-inch blocks that can be moved from one box to another over a partition in one minute. In the Action Research Arm Test (ARAT, Lang 2006), a measure of function, the robotic intervention produced significantly greater improvements than conventional therapy ( $p = 0.033$ ).

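### The Fugl-Meyer effect size of 1.9 and N=5 per group do not fit the planned equal arms: the same inputs give 1.24 and N=9, with no change to the planned enrolment

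*Combined protocol and SAP*

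**What the plan says.** The Power Analysis (Section 5, Study Design) builds the Hypothesis III calculation for the Fugl-Meyer from two sources. For the experimental arm: "The experimental treatment in our pilot study produced gains of 7 (sd=4.9) in the Fugl-Meyer". For the control arm: "A recent study reported gains of 2.47 (sd=1.67) on the Fugl-Meyer after 24 hours of conventional therapy in 35 stroke subjects". It continues: "Using these data, the mean difference in treatments will have an effect size of 1.9". For a 1-tailed unpaired t-test it then states that "N=5 subjects in each treatment group are needed to detect this difference with power > 0.80".

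The same section treats the ARAT in parallel: gains of 5.6 (SD 4.7) against 1.0 (SD 5.7, 17 subjects), effect size 0.84, N=19 per group. The ARAT figure is the larger, so it sets the trial size. After allowance for dropout of 0.167 the plan is to "recruit 23 subjects into each treatment group". The arms are therefore equal. The section does not say how the SDs were pooled for either outcome.

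**The concern.** The difference in gains is 4.53 points. An effect size of 1.9 needs a common SD of about 2.4, which is much nearer the control SD (1.67) than the pilot SD (4.9). In a trial with equal arms both SDs count equally in the variance of the difference, so a value that close to the smaller one suggests that the larger source study was given more weight. How many patients another study enrolled has no bearing on the precision of this trial's arms.

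What is at stake is whether the printed Fugl-Meyer effect size and sample size follow from the printed inputs, and whether the claim that 19 per group are enough for this outcome survives once they are corrected.

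**Working it through.** **Inputs.** From the Power Analysis: gains 7 (SD 4.9) and 2.47 (SD 1.67, n=35); 1-tailed unpaired t-test; power above 0.80; equal arms. Alpha of 0.05 is stated there only for Hypotheses I and II and is assumed to carry over.

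The number of robot-first pilot patients is not given. Section 4 (Background) says "Twelve chronic stroke subjects were randomized to 12 hours of robotic or conventional therapy and then crossed over to the other therapy type", so an even split would give 6. Section 4 also reports the Fugl-Meyer gain as 7 ± 2.2. If 2.2 is a standard error, (4.9/2.2)² = 4.96, which points to 5. Both are tried.

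**Step 1: reproduce the plan's figure.** Difference = 7 − 2.47 = 4.53.

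- Weighting by degrees of freedom, 6 pilot patients: SD = √[(5 × 4.9² + 34 × 1.67²)/39] = 2.35; d = 4.53/2.35 = 1.93.
- Weighting by n, 5 pilot patients: SD = √[(5 × 4.9² + 35 × 1.67²)/40] = 2.33; d = 1.94.
- Weighting by degrees of freedom, 5 pilot patients: SD = 2.24; d = 2.02, which does not match.

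The first two round to 1.9. With d = 1.9, noncentral-t power is 0.77 at 4 per group and 0.86 at 5, so the printed N=5 follows. The same two recipes give 0.840 and 0.838 for the ARAT, both rounding to the printed 0.84 with N=19. Size weighting therefore explains both printed effect sizes.

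Other ways of combining the Fugl-Meyer SDs do not give 1.9:

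| SD used | d |
|---|---|
| Pilot SD alone (4.9) | 0.92 |
| Root mean square, equal weights | 1.24 |
| Arithmetic mean of the SDs | 1.38 |
| Geometric mean of the SDs | 1.58 |
| Control SD alone (1.67) | 2.71 |

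**Step 2: the SD for equal arms.** With n per arm, the variance of the difference in means is (4.9² + 1.67²)/n. The two-sample formula writes this as 2·SD²/n, so

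SD = √[(4.9² + 1.67²)/2] = √[(24.01 + 2.79)/2] = 3.66, and d = 4.53/3.66 = 1.24.

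The weighting matters because the variances differ by a factor of 24.01/2.79 = 8.6.

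**Step 3: Fugl-Meyer power with d = 1.24, 1-tailed alpha 0.05.** Student t by the noncentral t distribution; Welch by simulation with the two unequal SDs.

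| N per group | Student t | Welch |
|---|---|---|
| 5 | 0.56 | 0.52 |
| 8 | 0.76 | 0.74 |
| 9 | 0.81 | 0.79 |
| 10 | 0.84 (simulated) | 0.83 |
| 19 | 0.98 | 0.98 |

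Nine per group are needed with the Student t-test, ten with Welch. Simulating the Student t-test with the unequal SDs gives 0.57 at 5 and 0.81 at 9, so the noncentral-t figures hold.

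**Step 4: Fugl-Meyer power at the planned 19 per group.** 0.98 for 1-tailed 0.05; 0.96 for two-sided 0.05; 0.92 for two-sided 0.025. The last is what a Bonferroni correction over the two timepoints in the Data analysis section would imply.

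**Step 5: the ARAT on its stated inputs with the same SD.** SD = √[(4.7² + 5.7²)/2] = 5.22; d = 4.6/5.22 = 0.88; N = 17 per group (power 0.81); power 0.85 at 19. Trial size: 19/(1 − 0.167) = 22.8, rounded up to 23, as planned.

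**The case against.** The strongest reply is that nothing in the design depends on N=5. The ARAT fixes 19 per group, and the plan's closing statement that 19 per group will detect the Fugl-Meyer difference remains true on these inputs. That stands, and it makes the point minor.

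A second reply is that a size-weighted pooled SD is a conventional form of Cohen's d, so the fault lies in the choice of method and the arithmetic itself is sound. That also stands in part: 1.9 and N=5 do reproduce. But such pooling suits two estimates of one common variance. Variances that differ 8.6-fold give no support for that, and the result was then applied to equal arms.

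A third reply is that the weighting is inferred. That is true, and so is the pilot size. The correction does not need the inference, because 1.24 follows from the printed means and SDs alone.

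Four stronger readings are tempting, and the documents do not support them:

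- A reader might infer that the trial is underpowered for the Fugl-Meyer. At 19 per group it is not.
- A reader might infer that the comparison was made to look several times as informative as it is. Required N rises 9/5 = 1.8-fold, and d² is overstated about 2.4-fold: (1.9/1.24)² = 2.35.
- A reader might infer that the Fugl-Meyer is the only outcome left to carry Hypothesis III. Equal weighting moves the ARAT the favourable way, from 0.84 to 0.88. Any separate doubt about the ARAT inputs would have to be shown on its own.
- A reader might infer that the analysis must switch to Welch. With equal arms of 19, both tests have power 0.98.

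**Conclusion.** The point holds as a minor correction. On the protocol's own inputs and equal arms, the Fugl-Meyer effect size is 1.24, so the printed 1.9 is about 53% too high (1.9/1.24 = 1.53). The required number is 9 per group (10 under Welch), where the plan prints 5, and 5 per group would have power of about 0.56 where more than 0.80 is claimed.

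These figures assume 1-tailed alpha 0.05 for Hypothesis III and take the quoted means and SDs at face value. The explanation of how 1.9 arose also assumes 5 or 6 pilot patients. Enrolment, completers per group and the planned tests are unaffected.

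**What to change.** In the Power Analysis:

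1. Replace the Fugl-Meyer effect size of 1.9 and N=5 with 1.24 and N=9 per group (1-tailed 0.05, Student t). State that the SD is the root mean square of the two group SDs. If Welch is the intended test, give 10.
2. Use the same SD for the ARAT on its stated inputs: effect size 0.88, N=17 per group, power 0.85 at 19.
3. State Fugl-Meyer power at 19 per group as 0.98 on the protocol's 1-tailed 0.05 basis. Give 0.96 two-sided alongside it, and about 0.92 two-sided with Bonferroni correction for two timepoints, each labelled with its alpha and sidedness.
4. State the alpha used for Hypothesis III.

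The cost is a few figures and a sentence or two. The ARAT remains the larger requirement, so 19 completers and 23 recruited per group can stay, and the analysis method does not change.

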Interestingly the robotic training appeared to facilitate the effects of conventional therapy. There were significant gains in the Box and Blocks after conventional therapy only if it was preceded by a period of robotic training ( $p = 0.044$ ). Clinically significant gains were present in the Fugl-Meyer when robot therapy was given first and followed by conventional therapy. The mean gain was  $7 \pm 2.2$  points, which was statistically significant ( $p = 0.034$ ). This gain was larger than 10% of full scale (6.6 points), which is considered the minimally clinically important difference (MCID) on this scale (Gladstone 2002, Lo 2010, Page 2012). In the ARAT, the gains at the end of treatment (robot + conventional) did not reach the MCID threshold of 10% or 5.7

points (van der Lee 1999, van der Lee 2001). However, gains following the first period of robot treatment did approach the MCID threshold (gain=5.6±2.1; p=.057).

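### The ARAT effect size that sets 19 per group uses the pilot's robot-only gain as if it were the full-treatment gain, so power above 0.80 for Hypothesis III is not supported

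*Combined protocol and SAP*

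**What the plan says.** The Specific Aim (section 3) defines the experimental treatment as 12 hours of robot therapy followed by 12 hours of conventional therapy. Hypothesis III compares its gains with those after 24 hours of conventional therapy.

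For that comparison on the ARAT, the Power Analysis (section 5) gives the experimental-arm input as: "Similarly for the ARAT, we had gains of 5.6 (sd=4.7) after the experimental treatment in our pilot study". It sets this against a published control gain of 1.0 (SD 5.7, n = 17), obtains an effect size of 0.84, and concludes: "For a 1-tailed unpaired t-test, N=19 subjects in each treatment group will detect this difference with power > 0.80". It then states that 19 per group will detect the expected pre-post changes and group differences in both the ARAT and the Fugl-Meyer, and inflates to 23 per group for dropout.

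Two other places describe the same pilot data:

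- Background (section 4), robot alone: "gains following the first period of robot treatment did approach the MCID threshold (gain=5.6±2.1; p=.057".
- Background (section 4), full treatment: "the gains at the end of treatment (robot + conventional) did not reach the MCID threshold of 10% or 5.7" points. No mean or SD is given.
- Power Analysis, Hypothesis I (robot alone): ARAT dz = 1.2.
- Power Analysis, Hypothesis II (robot plus conventional): ARAT dz = 0.77.

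**The concern.** The gain of 5.6 is assigned to two different time points. If it belongs to the first robot period, the Hypothesis III calculation subtracts a 24-hour conventional gain from a 12-hour robot-only gain, which is not the comparison the trial will make.

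The number matters because it fixes the sample size. The sample sizes derived in the Power Analysis are 8, 18, 16, 6, 5 and 19, and the 19 comes from this calculation alone. Hypothesis III is the randomised comparison. The ARAT is one of its three outcomes, and the plan says it has no pilot data to power the MAL. If the ARAT comparison is underpowered while the plan claims more than 0.80, a null ARAT result could be read as evidence of no benefit.

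**Working it through.** **1. Reproduce the plan's figure.** Inputs from the Power Analysis: gains 5.6 (SD 4.7) and 1.0 (SD 5.7, n = 17), one-tailed unpaired t-test. Alpha is stated as 0.05 one-tailed for Hypotheses I and II and is assumed to carry over to III.

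- Pooled SD weighted by degrees of freedom, pilot n = 6: √[(5×4.7² + 16×5.7²)/21] = 5.48, so d = 4.6/5.48 = 0.84.
- With pilot n = 5: √[(4×4.7² + 16×5.7²)/20] = 5.51, so d = 0.83.
- Noncentral t, d = 0.84, 19 per group: power 0.815, and 19 is the smallest n that reaches 0.80.
- 19/(1 − 0.167) = 22.8, hence 23 per group.

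The arithmetic from d = 0.84 onwards is correct. The question is the input.

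**2. Identify where 5.6 (SD 4.7) comes from.**

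| Check | Calculation | Compare with |
|---|---|---|
| Implied n if 2.1 is a standard error | (4.7/2.1)² = 5.0 | Fugl-Meyer: (4.9/2.2)² = 5.0 |
| SD from the Background figure | 2.1×√5 = 4.70 | SD 4.7 in the Power Analysis |
| p-value of the robot-only gain | t = 5.6/2.1 = 2.67 on 4 df, p = 0.056 | p = .057 in Background |
| Standardised gain | 5.6/4.7 = 1.19 | dz = 1.2 robot alone; dz = 0.77 full treatment |

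All the checks point to the robot-only period. The Fugl-Meyer input is a useful contrast: 7/4.9 = 1.43, which agrees with its full-treatment dz of 1.41. That line uses the right time point; the ARAT line does not.

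**3. Recompute with the plan's full-treatment figures.** The mean m and SD s after full treatment are not printed, but they must satisfy m/s = 0.77 and m < 5.7. For each m:

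- s = m/0.77
- d = (m − 1.0)/pooled SD, with the control SD at 5.7
- Pooled SD either weighted with pilot n = 5, √[(4s² + 16×5.7²)/20], or equally weighted, √[(s² + 5.7²)/2]
- Power from the noncentral t, one-sided 0.05, 19 per group

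| Mean m | SD s | d, weighted / equal | Power, weighted / equal | n per group for 0.80 |
|---|---|---|---|---|
| 3.6 (SD kept at 4.7) | 4.7 | 0.475 / 0.501 | 0.42 / 0.45 | 56 / 50 |
| 5.0 | 6.5 | 0.68 / 0.66 | 0.66 / 0.63 | 28 / 30 |
| 5.6 (mean kept) | 7.3 | 0.76 / 0.70 | 0.74 / 0.69 | 23 / 26 |
| 5.7 (ceiling) | 7.4 | 0.77 / 0.71 | 0.756 / 0.694 | 22 / 26 |

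Power rises with m over this range, so the last row is an upper bound. Weighting with pilot n = 6 gives d = 0.764 and power 0.748 at the ceiling.

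**The case against.** The strongest reply on the numbers is that the documents fix only the upper bound. Power of 0.42 to 0.45 assumes that the SD stayed at 4.7 after the second treatment period, which nothing in the plan states. That is right. The firm statement is that power is at most about 0.76, and the lower figures are illustrations.

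The full-treatment mean might also have been about 5.6, which would make the label correct. In that case dz = 0.77 requires an SD of 5.6/0.77 = 7.3, so the SD of 4.7 would be wrong, and power would be 0.69 to 0.74. No reading reconciles 5.6, 4.7 and 0.77.

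It can also be said that the design hardly depends on this figure, because the Fugl-Meyer calculation for Hypothesis I already needs 18 in the experimental arm (power 0.914 at 18, 0.899 at 17). This stands as a limit on scope. The Hypothesis I and II sample sizes and the Fugl-Meyer comparison do not use the mislabelled number. It does not rescue the stated ARAT power.

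Finally, dz = 0.77 is itself an imperfect input. The pilot had a one-month washout between therapies (section 4), whereas here conventional therapy follows immediately (section 5, Overview), and about five pilot patients contribute. The restated figure should carry that caveat. It is still the only full-treatment ARAT effect the plan reports.

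**Conclusion.** The concern holds. The ARAT input to the Hypothesis III calculation is the pilot's robot-only gain, mislabelled as the gain after robot plus conventional therapy. On the plan's own full-treatment figures, power at 19 per group is at most about 0.76, against a stated value above 0.80, and could be near 0.42. The sample size that would restore 0.80 is at least 22 per group and cannot be fixed more closely from the documents.

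This rests on dz = 0.77 and a mean below 5.7 as printed, the plan's control figures, 19 analysed per group, and a one-sided 0.05 test. The last assumption favours the plan: even at d = 0.84, a two-sided 0.05 test has power of about 0.71, and the Bonferroni correction in the Data analysis section would lower it further.

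The Fugl-Meyer comparison is not affected. With equally weighted SDs, d = 4.53/√[(4.9² + 1.67²)/2] = 1.24, and power at 19 per group is 0.98.

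**What to change.** In the Power Analysis, Hypothesis III paragraph:

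1. Replace 5.6 (SD 4.7) with the pilot's ARAT mean gain and SD at the end of robot plus conventional treatment, that is, the data behind dz = 0.77, and give the number of patients.
2. Recompute the effect size against 1.0 (SD 5.7), state how the SDs were pooled, and restate ARAT power at 19 per group.
3. Note that the pilot's washout differs from the present schedule.
4. Delete or qualify the claim that 19 per group will detect ARAT group differences. The plan can say that its pilot figures support the Fugl-Meyer comparison at this size. That sentence is optional.

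The cost is a rewording from data the sponsor already holds. Enrolment can stay at 46 and no procedure changes. The stated ARAT power becomes less favourable.
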